#### *4.5 Timeline*

Upon opening of the study, we expect to recruit approximately 2-3 participants per month for 16 months. Data will be entered as they come in; some metabolic biomarker assays will be performed from fresh samples and some will be performed in batch upon collection of the last sample. Data analysis will take place in the subsequent months. These data will be used to inform follow-on randomized controlled trials. It is our goal that at least two manuscripts—one describing the patient-reported outcomes and one describing the metabolic outcomes—will be submitted for publication within one year of the study closing. It is also likely that a third mixed methods manuscript describing dietary habits and preferences of patients undergoing chemotherapy will arise from the exit interviews at the end of the study.

#### *4.6 Design considerations*

**Why the Mediterranean Diet?** The Mediterranean Diet is one of the most common dietary plans that is studied by nutrition researchers and has shown large health benefits, especially for cardiovascular disease. The diet is appealing for researchers and for the public because it is relatively easy to implement—many of the meals are common in American culture and it is not too restrictive. In general, the meals are very appetizing. The Mediterranean Diet has components that are particular beneficial to metabolism such as high fiber, low glycemic index, and rich in micronutrients such as polyphenols,  $\alpha$ -lipoic acid, and B vitamins.

**Why during chemotherapy?** An intervention during chemotherapy, rather than after, could substantially prevent both reversible and permanent chemotherapy-related metabolic dysfunction that contributes to cancer-related fatigue. Indeed, while some metabolic toxicity is reversible, some can persist long into survivorship (longest follow-up thus far: 6 years). Also, a cancer diagnosis is often seen as a “window of opportunity” for behavior change including exercise and smoking cessation, though less research has been done for nutrition. From a psychological standpoint, during cancer treatment, food sometimes shifts roles from pleasure to medicine, motivating some patients to make healthy choices and empowering them to take charge of that aspect of their life. Dietary interventions have been implemented successfully during and after chemotherapy treatment, though it is unclear which treatment stage is “best” for attenuation of fatigue or other supportive care outcomes.

Behavioral interventions such as exercise tend to confer the largest benefits for symptoms in survivorship vs. during treatment, but this is because patients’ symptoms are naturally improving after cessation of treatment. Longer follow-up time points are needed to evaluate whether an intervention during vs. after chemotherapy will lead to overall less symptom burden. Also, it is our hope that patients will learn new healthy recipes and eating patterns that are sustained into survivorship.

**Why a randomized clinical trial and not a single arm feasibility study?** In order to evaluate the effects of the Mediterranean Diet on cancer-related fatigue, a control group is required to assess the change in fatigue over time without the intervention. If we determine that this study is not feasible and participants in the intervention group do not follow a Mediterranean Diet, we will still have important longitudinal data to correlate fatigue measures with diet metrics and metabolic measures over the course of chemotherapy.

**Why randomize 2:1?** Participants who sign up for a nutrition intervention study are often motivated to make dietary changes. By randomizing 2:1, each participant has a larger chance of getting the intervention and fewer participants will be disappointed not to receive the intervention right away. This ratio will still give us enough power (with n=42 participants total) to detect changes in fatigue. In addition, uneven allocation will provide us with more data about the intervention without increasing our sample size.

**Why provide food?** Meal planning, grocery shopping, and preparing food are large barriers dietary change, especially during chemotherapy. We believe that if we overcome these barriers to consuming the Mediterranean Diet at the onset of the intervention while we provide education, we will have greater adherence. In addition, meal provision is an established technique to facilitate behavior change, as people learn types of food that fit within the diet and serving size.

**Why include patients with underlying metabolic disorder? Will it reduce the ability to detect changes?** Diabetes is the most common metabolic disorder, and at least 15-20% of patients have diabetes as a co-morbidity with their cancer. The literature on the interaction between metabolic disease and supportive care outcomes is in its infancy, and while these conditions are complex, heterogeneous, and ever-changing, there are possible overarching interactions that could be curtailed with dietary interventions. We would like to recruit people with and without metabolic disease to ensure that this intervention is feasible among both, and in the future we would like to further investigate the specific interactions between cancer, preexisting metabolic disease, and cancer-related fatigue.

## 5. Inclusion and exclusion criteria

Participants will be selected to represent a broad range of patients with varying demographics (e.g., age, race), and incoming metabolic functioning (e.g., diabetes). This study will not be powered for any subgroup analyses. Participants will be excluded who have dietary allergies or intolerances (e.g., celiac disease), because the diets will be standardized and we do not want to inadvertently introduce any allergens or triggers.

Inclusion criteria (Participants must...):

1. Have a diagnosis of stage I-III cancer,
2. Be scheduled to receive chemotherapy and have at least 6 weeks remaining,
3. Be able to speak English,
4. Be at least 18 years old,
5. Be willing to adhere to study procedures, and
6. Be able to provide written informed consent.

Exclusion criteria (Participants must not...):

1. Be on enteral or parenteral nutrition,
2. Be pregnant (confirmed by pregnancy test at the start of chemotherapy treatment), as pregnant women have different nutrition needs than non-pregnant women,
3. Have a brain tumor,
4. Have any plan to get radiation to the head,

5. Have specific dietary needs that a Mediterranean Diet cannot meet (e.g., allergies to nuts, gluten intolerance), or already be following the Mediterranean Diet (i.e., have a score  $\geq 10$  on a modified 14-item Mediterranean Diet questionnaire).

Patients who are following a vegetarian or vegan diet will be eligible because it is possible to adhere to the Mediterranean Diet without eating meat or animal products. None of our study participants have to eat the food we provide (meat, animal products, or other food), and our study dietitian is available to all of our participants to help find appropriate substitutions and protein sources. (Participants will “lose” a point on the adherence questionnaire for not eating fish, but they do not need to obtain a perfect score to be considered adherent.)

Patients who have 6 weeks remaining will be eligible to participate in this 8-week trial because fatigue often persist for 2 weeks or more after a chemotherapy infusion. Indeed, these two- to three-week recovery periods are built into some chemotherapy regimens. We are incorporating this “recovery” period into the eligibility and study timeline. For example, a person that has their last infusion scheduled 6 weeks away will be eligible.

## **6. Recruitment methods**

### *6.1 Identification and recruitment*

Participants will be recruited using the Cancer Control group’s established procedures. Before recruitment, approval will be obtained by the Cancer Control Disease Working Group, the James P. Wilmot Cancer Institute Clinical Trials Peer Review and Monitoring Committee (PRMC), as well as the University of Rochester Medical Center (URMC) Research Subject Review Board (RSRB). Potential participants will be identified using three methods: (1) screening medical records, (2) direct referral from providers (e.g., nurses and physicians), and (3) flyers.

#### *6.1.1 Identification and recruitment via medical records*

Potentially eligible participants will be identified in a HIPAA-compliant manner by study personnel via review of scheduled outpatient appointments. The study team will then review any potential candidates. Medical records typically show a recent pregnancy test, presence of metastases, dietary allergies, and any current or recent use of enteral or parenteral nutrition. If a patient appears to be eligible, the study team will contact the treating physician to notify them of a potential candidate and obtain approval to speak with the patient. The physician or another clinical staff member will initially assess whether the participant has any interest in participating in a clinical trial to investigate a dietary intervention and cancer-related fatigue. If the patient is interested, the provider will refer the individual to the study team. Our team will meet with the patient to discuss the study or send information about the study via mail or myChart with our contact information. The study team will then meet with the candidate (immediately after their oncology appointment or at a later date; in person or via phone or computer) to discuss the study activities in detail and review eligibility. If the patient is eligible, study personnel will explain the details of the study and obtain informed consent from those who agree to participate (paper-based or eConsent). If the person is eligible and gives informed consent, a baseline/randomization appointment will be scheduled. At this point they will be given a 3-day food record to bring completed to the baseline assessment and the baseline questionnaires (or access to the questionnaires via REDCap).

#### *6.1.2 Identification and recruitment via direct referral from nurses and physicians.*

We are working with several oncologists (including, but not limited to, our co-investigators Drs. [name] and [name]) and their medical team (e.g., nurses, physician assistants) to identify potential patients at the University of Rochester who are likely eligible for our study. If the patient is eligible based on information in the medical records and from the physician and medical team, we will request that the physician refer the patient to us (or obtain the physician's permission to contact the patient) to discuss our study.

#### *6.1.3 Flyers*

We designed a flyer that will be placed in locations designated for such use that advertises our study. Patients with a recent diagnosis of cancer can contact us directly for more information. We will contact their treating oncologist to ensure the patient meets eligibility criteria before consenting them.

### *6.2 Screening*

For convenience to the patient, we will make every effort to combine the patient's clinic appointment with study assessments. To protect the privacy of potential subjects, we will conduct recruitment discussions in a private location.

[name] or a member of the study team will meet the patient (in person or remotely) to explain the project and invite them to participate. We expect that some patients will decline to participate, and we want to ensure that we not approach the same patient twice. Therefore, we will keep a screening log containing the following information:

- Screening ID (1, 2, 3...)
- Name
- Date of contact
- Medical record number
- Where/how we talked to the patient (e.g., clinic location, phone)
- Whether the patient was eligible or not
- If ineligible, the reason they are ineligible
- Whether the patient ultimately consented or declined
- If declined consent, the reason for declining consent
- If consented, the subject ID in the study (e.g., 101, 102, 103, ...)

We will obtain permission to approach and confirm with the treating medical oncologist that they are appropriate for the study prior to discussing the study with patients.

## **7. Consent process**

### *7.1 Written consent*

For participants who are interested in participating, a member of the study team will meet with the potential participant in a private room. She or he will go through the consent form with the patient face-to-face to ensure comprehension. They will then be given the option to sign the consent form. [name] (study chair) will be available to answer any questions the potential participant may have about any aspect of the study prior to consenting and throughout the entire study period. The participants will also have access to the registered dietitians at the Integrative Oncology and Wellness Center at Pluta Cancer Center

(e.g., [name], RD) if they have other diet-related questions. Potential participants will be allowed to take the consent form home to think about and discuss with family or friends; each potential participant will have sufficient time to consider participation. To minimize coercion, the study team will emphasize that participation is completely voluntary and their cancer care will not be affected by their participation in the study.

### *7.2 eConsent*

In lieu of the paper-based consent document, consent may occur remotely using the RSRB-approved eConsent document provided via REDCap. The study staff will screen for potential participants using the above screening procedures and initiate contact via the following methods: 1) the treating oncologist or a member of the medical team (e.g., nurse practitioner) will introduce the study to the participant via a clinic appointment (in person or telehealth) and inquire if it would be okay for our study team to contact them, 2) with approval of the treating oncologist or a designee, a recruitment letter will be mailed to the potential participant briefly describing the study and asking them to contact us if they would like more information, and 3) with approval of the treating oncologist or a designee, a message will be sent to the potential participant via eRecord (myChart) briefly describing the study and asking them to contact us if they would like more information. If a potential participant is interested, the study team will talk to the person on the phone and obtain verbal permission from the patient to send a copy of the eConsent via email or text message stating, “Because URMC can’t control the security of email or text messages once we send them, we need your permission to text or email you. Do you want to receive a copy of the consent document and a link to the eConsent via text or email?” Verbal permission from the patient will be documented. We will email or text the eConsent in the form of a pdf document and set up a phone call or Zoom meeting (participant’s choice) to formally go over the consent document. In a separate email or text, we will provide a link to the eConsent document as well as instructions on how to access the eConsent—we will use verification with a passcode based on known information (e.g., the patient’s home zip code). No personal health information will be sent via any emails/texts. The eConsent documents may be viewed on computers, electronic tablets, or smartphones. The pdf copy of the eConsent and the REDCap eConsent will have identical information; it will be optional for the person to review the consent before the study team discusses it with them. After a member of the study team reviews the consent document with the participant over the phone or computer, they will have the opportunity to electronically sign the eConsent via REDCap. The person obtaining consent will initiate the eConsent process from within REDCap for their name and a timestamp to appear on the study participant’s signed consent form. Once the eConsent form is signed and submitted, the patient and/or legally authorized representative will be able to receive a print out of the paper copy, download a pdf, and/or receive an email with a PDF attachment of the signed consent form.

### *7.3 The consent document*

The informed consent document will provide consent for the entire study, though consent may be withdrawn at any time. Because this study includes only one “phase,” we will not ask participants to re-consent during the study. The consent form will also contain information regarding HIPAA authorization, if participants consent to be contacted for future research studies, preferred method of contact (i.e., phone, text, email).

For individuals who are eligible and who provide informed consent, the following information will be entered into a secure electronic database (e.g., Excel on a password-protected computer). This information is needed in case contact is required after the study and/or the participant requires payment through the mail.

- Participant ID number (used to identify the subject on all study forms and notes)
- Name
- Subject phone number
- Subject email address
- Medical Record number
- Date of informed consent
- Date of registration

If a participant requests to waive or alter elements of the informed consent document, they will not be allowed to participate in the study; the one exception is that they do not need to provide consent to using email communication to participate in the study. Similarly, if a patient requests to waive documentation of consent, they will not be allowed to participate. We will reiterate that the only record linking the subject and the research would be the consent document and the principal risk would be potential harm resulting from a breach of confidentiality. If a patient waives or alters HIPAA Authorization, the patient will also not be allowed to participate. We will explain why the study cannot be conducted without the use or disclosure of protected health information (PHI), and describe the plan to protect identifiers from improper use and disclosure. We will explain that all forms will be held in a locked location for at least 6 years, and disposal of forms will occur in a confidential manner. PHI will not be reused or disclosed to any other person or entity except (i) as required by law, (ii) for authorized oversight of the research study, or (iii) for other research for which the use or disclosure of PHI would be permitted by the HIPAA Privacy Rule.

## **8. Study procedures**

### *8.1 Overview of study*

We will be conducting a pilot randomized clinical trial testing the preliminary efficacy of an 8-week Mediterranean Diet intervention during chemotherapy to prevent cancer-related fatigue among patients with cancer. We will also gain mechanistic insight into cancer-related fatigue and the ability of the Mediterranean Diet to modulate it via a thorough assessment of metabolic parameters. Participants in the intervention arm will receive education regarding the Mediterranean Diet with respect to its components, purported health benefits, and specific guidelines for implementation. In order to improve adherence, in weeks 1-4, participants will receive food (approximately 1,600 kcal/day) compliant with the Mediterranean Diet. All participants will complete questionnaires and provide blood at baseline, 4 weeks, and 8 weeks.

### *8.2 Study procedures, assessments, and participant activities*

#### *8.2.1 Screening procedures*

A pregnancy test at the start of chemotherapy is the only test that is needed for screening (and only for females who are pre-menopausal), and this is part of standard care for cancer treatment and should be in the medical record. A history of a hysterectomy or tubal ligation is also acceptable to determine if a woman is not pregnant. All other exclusion criteria—needs for enteral or parenteral nutrition, metastases to the head, plans to have radiation to the head, dietary allergies, dietary intolerances, specific dietary needs—are included in the medical record or will be known to the patient. Thus, eligibility will usually be apparent before the consent form is provided to the patient. If there are any screen failures, we will retain the information in a screening log as described in §6.2 to avoid approaching them again.

#### *8.2.2 Source of record or measures*

The Clinical Record contains weight, height, current menopausal status, Karnofsky Performance Status (KPS) or Eastern Cooperative Oncology Group (ECOG) Performance Status, comorbidities, cancer stage, surgical procedures, types and doses of treatments, and other clinical characteristics. The study team will use the medical record to complete as much of this as possible. All other questionnaires will be completed by the participant, and all other measures will be obtained by the study team with the participant or the participants' blood samples.

#### *8.2.3 Research registration*

Documentation of study participation will be included in OnCore for those subjects enrolled in the research study.

#### *8.2.4 Assessment locations*

The assessments will take place in one of two locations: 1) at the clinic, and 2) at home (or wherever is convenient for the participant). The blood draws will take place at the clinic, which comprises the Wilmot Cancer Institute, Pluta Cancer Center, or a UR Labs Patient Service Center. The questionnaires will be completed via REDCap (or, alternatively, paper-based, if the participant prefers) and can be completed at the clinic or at home (or wherever is convenient). The consent will be completed at the clinic or remotely.

#### *8.2.5 Randomization procedures*

Randomization will be revealed to the participant at the end of the baseline assessments, before delivering the instructional portion of the intervention.

We will employ two treatment arms in a 2:1 allocation ratio:

1. Mediterranean Diet: an 8-week intervention entailing education of the Mediterranean Diet and delivery of Mediterranean Diet-inspired meals for 4 weeks.
2. Usual care: completion of assessments, with no intervention and usual care for their cancer.

Consented subjects will be randomized with a computer-generated random numbers table with block sizes of 3 and 6 and stratified based on how frequently they will be receiving chemotherapy (weekly, biweekly, or every 4 weeks vs. other). The random numbers tables will be generated centrally by [name], the project biostatistician, or a designee. A total enrollment of 42 subjects is planned.

Participants cannot be blinded due to the nature of the intervention. PI blinding is also not feasible given that the PI will play an active role in recruitment, intervention delivery, data acquisition, and analysis.

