dose delays or changes to the chemotherapy schedule, we will still collect assessments at the originally planned time.) We estimate attrition between approximately 20 and 25%, thus we estimate to retain 33 (22:11) evaluable patients. This sample size is appropriate for small randomized pilot studies and it will allow us to obtain preliminary estimates of descriptive statistics [mean, standard deviation (SD), and confidence intervals (CI)]. The primary endpoint is the change in fatigue as measured by FACIT-F from baseline (T1) to 4 weeks (T2). Assuming a correlation of 0.50 between T1 and T2 FACIT-F measurements, a total sample size of n=33 will provide 80% power at the 0.15 two-sided significance level to detect an effect size (ES, standardized mean between-group difference) of 0.75 of the intervention effect on change in T2-T1 FACIT-F using analysis of covariance (ANCOVA) with T1 FACIT-F as a covariate (**Fig. 3**). The estimates of T1-T2 correlation and attrition rate are based on our prior studies.

Feasibility is often determined for nutrition interventions among 10-15 participants (e.g.,); pilot preliminary efficacy studies usually recruit 20-30 (e.g.,). **Table 6** below shows prior studies that are similar to this one, including their sample size.

Study	n	Population	Intervention	Outcome	Results
Zick et al. (2017) 	30	breast cancer survivors	Fatigue reduction diet vs. General Health Curriculum (time and attention control) for 3 months	Brief Fatigue Inventory	From baseline to 3-months, fatigue improved by 44±39% in diet group compared to 8±34% in the control group (p=0.01)
Skouroliakou et al. (2018) 	70	breast cancer survivors	Mediterranean Diet for 6 months vs. handout	serum antioxidant capacity and body composition	The dietary intervention based on Mediterranean Diet improved serum antioxidant capacity, body composition, and glycemic profile.
McMillan et al. (2011) 	27	healthy women in their 20's	Mediterranean Diet vs. control for 10 days	Profile of Mood States	A group × time interaction demonstrated that the Mediterranean Diet reduced fatigue (p=0.16) and improved vigor (p<0.01).

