### *17.2 Data Handling, Rigor, Quality, and Reproducibility:*

Data will be entered in REDCap electronic forms and electronically collated in a HIPAA-compliant REDCap database managed by our Division. After collation, data will be audited electronically and visually, as needed, for errors. Appropriate graphical or statistical diagnostics methods will be employed in each of the analyses to evaluate distribution of variables (e.g., to identify shape of the distribution and outliers) and also to evaluate the model assumptions (e.g., if deviation from the statistical assumptions is found, we will use alternative methods such as transformations or nonparametric analyses). Outliers that are detected will be investigated to determine if they are due to error. If not, analyses will be conducted with and without them to assess sensitivity. Because this is a preliminary efficacy study, unless stated otherwise, all hypothesis testing will be at the two-sided 0.15 level as appropriate for screening trials. SAS, JMP, and/or R software will be used for the analyses. Following the intent-to-treat principle, all randomized survivors will be analyzed in the arm as allocated, regardless of their compliance with the intervention or Mediterranean Diet contamination in the control group.

Although participants will be randomly assigned, differences may be present between study arms on demographic or clinical variables. Study arms will be compared on baseline demographic (e.g., age), clinical (e.g., cancer diagnosis, type of chemotherapy), and behavioral (e.g., physical activity, smoking) variables. If significant imbalance is found for a variable, it will be included as a covariate in subsequent analyses following standard practice.

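### Section 17 leaves several data-dependent analysis choices without thresholds while an unblinded PI takes part in analysis; the primary fatigue analysis should be frozen before arm is linked to outcomes

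*Combined protocol and SAP*

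**What the plan says.** **Roles.** The trial is open label. Section 8.2.5 says the PI cannot be blinded because "the PI will play an active role in recruitment, intervention delivery, data acquisition, and analysis". The random numbers tables come from "the project biostatistician, or a designee". No section says who runs the primary model, or whether that person sees arm.

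**What is fixed.** Section 17.1 names the change in FACIT-F from baseline to 4 weeks as the primary endpoint. Section 17.4.2 gives the model: ANCOVA of the 4-week fatigue score on arm and baseline score. Section 17.2 sets the level: "all hypothesis testing will be at the two-sided 0.15 level as appropriate for screening trials".

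**What is open.**
- Assumptions (17.2): if a deviation is found, "we will use alternative methods such as transformations" or nonparametric analyses. No criterion for a deviation is given.
- Outliers (17.2): analyses are run with and without them, as a sensitivity check. No definition is given.
- Covariates (17.2): "If significant imbalance is found for a variable, it will be included as a covariate in subsequent analyses following standard practice". The variables are listed by example only. Section 17.4.2 adds further covariates, also by example.
- Missing data (17.3): if a large proportion is missing, sensitivity analyses such as multiple imputation are run, and complete-case results are reported if the estimates are similar. Neither condition is quantified.

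**The concern.** Contact with participants prevents blinding of care. It does not require that modelling decisions be taken with arm visible, because analysis can be separated from delivery. As written, a person who knows the allocation may take part in deciding whether to transform, which points are outliers and which covariates to add, with no written threshold to hold the decision to.

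The 15% level describes one model chosen without sight of the treatment effect. If the model can follow the result, the fatigue comparison has a larger false-positive rate than stated. Section 17.4.2 says these results will be used to plan a future randomized trial. At 15% the test is already lenient.

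The imbalance rule raises a second, separate problem: it is a poor way to choose covariates even when followed faithfully.

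**Working it through.** **Step 1. The plan's own figure.** Section 17.1 states that "a total sample size of n=33 will provide 80% power at the 0.15 two-sided significance level". The target is a standardized difference of 0.75 and the assumed correlation is 0.50, with 22:11 evaluable patients.
- Standard error in SD units: √(1 − 0.5²) × √(1/22 + 1/11) = 0.866 × 0.369 = 0.320.
- 0.75 / 0.320 = 2.345. The normal critical value for two-sided 0.15 is 1.440.
- Power = Φ(2.345 − 1.440) = 0.817. With the noncentral t on 30 df it is 0.806.

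The stated 80% reproduces.

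**Step 2. How often the imbalance rule would act.** Section 17.2 puts all testing at 0.15 unless stated otherwise, so I take the imbalance tests to be at that level. The section gives five example variables. If they are independent, the chance that at least one is flagged by luck is 1 − 0.85⁵ = 56% (39% with three variables, 62% with six).

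**Step 3. The rules followed mechanically.** These are null trials, 6,000 per row, 22:11, correlation 0.5, two-sided 0.15. Assumptions not in the documents: the number of covariates and their weight on the outcome, imbalance tested at 0.15, and a Shapiro test at 0.05 leading to rank ANCOVA. Entries are rejection rates in percent. The simulation error is about √(0.15 × 0.85 / 6000) = 0.5 percentage points.

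| Covariates, weight | Fixed ANCOVA | Imbalance rule | Assumption rule | Both rules |
|---|---|---|---|---|
| 3, 0.2 | 14.9 | 13.6 | 15.1 | 13.8 |
| 6, 0.1 | 15.3 | 14.6 | 15.6 | 14.8 |
| 6, 0.2, heavy tails, t(4) | 15.1 | 12.3 | 15.5 | 12.6 |
| 6, 0.3 | 15.8 | 9.2 | 15.9 | 9.3 |
| 3, 0.4 | 15.2 | 9.7 | 15.5 | 9.9 |

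The assumption rule leaves the error rate where it was. The imbalance rule lowers it, because it adjusts in the trials where chance imbalance would have produced false positives and leaves an over-large residual variance in the others. For the same reason it uses prognostic information only when imbalance happens to occur, so it has less power than fitting the same prognostic covariates every time.

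The missing-data rule was tested on 3,000 null trials with 42 randomized, 9 missing at random and multiple imputation. Similar was defined, by assumption, as estimates within 0.2 SD. The rejection rate was 13.8% and 14.5% in the two settings tried.

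**Step 4. The most favourable version kept.** The setting is the same, but the smallest p-value is retained. An outlier is taken to be a studentized residual beyond the cut-off shown.

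| Versions compared | Cut-off 3 | Cut-off 2.5 | Cut-off 2 |
|---|---|---|---|
| ANCOVA, rank ANCOVA, outliers excluded | 19.2 | 21.8 | 27.7 |
| Those three, plus imbalance-adjusted and three added covariates | 24.8–27.8 | 27.1–31.6 | 31.9–37.4 |

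Across sets of three or four versions the range is about 19 to 30%. Choosing between only two versions gives 16–19% (imbalance-adjusted), 17–20% (rank), 17–29% (outlier exclusion, by cut-off) and 15–18% (complete-case or imputed).

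**The case against.** The strongest reply is that the plan contains no licence to pick the best p-value.
- The outlier runs are sensitivity analyses; both are done and neither replaces the other.
- Rank or transformed methods apply only if assumptions fail. With rank ANCOVA available only after a failed Shapiro test at 0.05, even opportunistic choice between it and the planned ANCOVA rejected 15.3%, against 18.6% under free choice.
- The imbalance rule looks only at baseline data.
- Endpoint, time point, model and level are fixed.
- The primary aim is feasibility, judged by the 70% criteria in section 17.4.1, and no go/no-go rule rests on the fatigue p-value.

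All of this stands. It rules out a stronger reading that a reader might infer: that the person who delivers the diet runs the analysis under several result-dependent rules, so that the true error rate is nearly double the stated 15%. The documents do not support that. Only the rule in section 17.3 compares treatment estimates. Section 4.3.1 allows trained staff as well as the study chair to deliver the intervention. Section 8.2.5 gives the PI an active role in analysis, not the sole or deciding one.

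A practical objection also stands in part. Withholding the arm column would not mask the PI, who helps deliver the intervention and could recognise participants by the ID and initials carried in the databases (section 14.1.1). This is a reason for someone else to hold the file, not a reason to leave the rules open.

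What the reply does not answer is that the thresholds are absent, that nothing says which result is the headline once a covariate is flagged, and that the caution at the end of section 17.4.4 refers to secondary and exploratory analyses.

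**Conclusion.** The point holds as a gap in specification. An unblinded PI takes part in analysis, and four data-dependent choices have no thresholds; one of them depends on treatment estimates.

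Followed mechanically, the rules cause no meaningful inflation. The imbalance rule moves the 15% test to between 9.2% and 14.6% in the runs shown and gives up power when the covariates are prognostic. Selecting the most favourable version with arm in view could raise the error rate to about 19–30%, and to 37% with five versions and an outlier cut-off of 2. Those figures are a worst case that the plan does not authorise. They depend on assumed cut-offs, covariate counts and weights, and should be quoted only as a range.

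For a 42-patient pilot this is a desirable improvement, not a defect that undermines the design.

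**What to change.** 1. In section 17.4.2, name the baseline-adjusted ANCOVA of 4-week FACIT-F fatigue as the single primary result and label every other version as sensitivity or exploratory.
2. In section 17.2, replace the significance-tested imbalance rule with a short list of prognostic covariates fixed in advance, for example the chemotherapy-schedule stratum already used in randomization. Keep the list short at 33 evaluable patients, since weak covariates cost degrees of freedom. Baseline characteristics can still be tabulated by arm without testing.
3. Before arm is linked to outcomes, write down the outlier definition, the criterion and method for transformation or rank analysis, and the missing-data method. The missing-data method needs the most care, because comparing estimates for similarity requires arm.
4. State that the project biostatistician, not the PI, holds a file without arm, makes any remaining decisions on it, then merges arm and runs the frozen code. That file should leave out participant initials and the Mediterranean Diet score, which could suggest arm. Distribution checks can use a model without the arm term.

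The cost is SAP wording, file handling and some biostatistician time (section 8.2.5 gives that role only the randomization tables). The PI also waits a little longer before exploring data by arm. Sample size and participant procedures do not change.
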